## 1.5 Rationale for Stage 2 Changes

All treatment arms in Stage 1 of PRM-151G-101 met the pre-specified efficacy criteria of  $\geq 1$  response to be considered for continued evaluation in Stage 2. Key findings from Stage 1 that led to the changes for Stage 2 are listed below.

- Overall response rate was 43% at 24 weeks and 50% at 36 weeks
  - At 36 weeks of treatment
    - 10 Bone Marrow responses
    - 4 IWG Symptom responses

- 10/17 subjects with baseline Hgb < 10 g/L and/or PLT < 50 x 10^9/L showed improvement in Hgb and/or PLT
- There was no apparent difference in efficacy or safety between PRM-151 administered once a week or every four weeks
- Hematologic improvements were more common with PRM-151 alone
- Most subjects had improvements in symptoms and modest reductions in splenomegaly, although not meeting IWG response criteria
- PRM-151 was very well tolerated both as a single agent and added to ruxolitinib, although adverse events were more common in the subjects also receiving ruxolitinib

Based on these results, the following changes have been made for Stage 2:

Design element	Stage 1	Stage 2	Rationale
Primary Objective	Evaluate the efficacy of two different dose schedules of PRM-151 in intermediate-1, intermediate-2, or high risk subjects with PMF, post-PV MF, or post ET-MF who are not receiving therapy for MF, and in subjects with PMF, post-PV MF, or post ET-MF on a stable dose of ruxolitinib for at least three months.	To determine the effect size of three different doses of PRM-151 on reduction in bone marrow fibrosis by $\geq$ 1 grade in intermediate-1, intermediate-2, and high risk subjects with PMF, post-PV MF, or post ET-MF who are anemic or thrombocytopenic and who are ineligible for, intolerant of, or have had an inadequate response to ruxolitinib.	Single agent efficacy at 10 mg/kg every 4 weeks supports continued evaluation  Identification of minimal effective dose is important for further development  Translational data suggests equal to greater efficacy at lower doses
Primary Endpoint	Percent of subjects with IWG-MRT response or reduction in bone marrow fibrosis by $\geq$ 1 grade	Percent of subjects with reduction in bone marrow fibrosis by $\geq$ 1 grade	Reduction in bone marrow fibrosis is most closely linked to the mechanism of action of PRM-151; assessment of clinical benefit related to decreased fibrosis, including IWG-MRT responses, will be done via secondary endpoints

Secondary Endpoints	Safety Change in bone marrow fibrosis Change in symptoms Duration of response PK	Safety Change in bone marrow fibrosis Improvement in hemoglobin Improvement in platelets Improvement in symptoms IWG-MRT response rate Duration of improvements	Individual assessment of disease related abnormalities will help to define the clinical benefit of PRM-151 and guide future clinical trials
Eligibility	Intermediate-1, 2, or high risk  Myelofibrosis Grade 2 or 3	Intermediate-1, Intermediate-2 or High risk  Myelofibrosis Grade 2 or 3  Not candidates for ruxolitinib based on EITHER  Hgb < 100 g/L and requiring at least 2 units PRBC in the 12 weeks prior to study entry and intolerant of or had in adequate response to ruxolitinib OR  PLT <50 x 10  /L	Subjects with clinically significant anemia or thrombocytopenia had the greatest benefit in Stage 1, and will provide the best opportunity to define the clinical benefit of PRM-151  Limiting eligibility to subjects who are not candidates for ruxolitinib ensures that we are enrolling subjects with the highest unmet need
Duration	24 weeks	36 weeks	Improvements in bone marrow fibrosis, hemoglobin, and platelets were all greater at 36 weeks than at 24 weeks, suggesting that PRM-151 effects improve over time and that clinical benefit may be underestimated at

			24 weeks. There is insufficient data at present to indicate that a longer study duration is required, but longer term data obtained from study extensions will be informative for future trials
Single agent or combination with ruxolitinib	Single agent AND added to a stable dose of ruxolitinib	Single agent	Hematologic improvements were more apparent in subjects on single agent PRM-151; dosing ranging can be done best with single agent. Future studies will assess PRM-151 in combination with ruxolitinib
Dose	10 mg/kg	0.3, 3, and 10 mg/kg	Efficacy has been observed in clinical studies at 1, 5, and 10 mg/kg, but recent dose ranging studies in rats and mice and IC50 data from in vitro studies suggest an effective dose range in humans of 0.2-10 mg/kg.
Schedule	Every week AND every 4 weeks	Every 4 weeks	No apparent difference in efficacy or safety between schedules in Stage 1
Randomization	No	Yes, randomized, blinded and stratified	Eliminating weekly dosing makes randomization and blinding possible, reducing bias and

			
increasing the rigor of the study.
 
Stratification allows for independent assessment of anemic and thrombocytopenic subjects.

Control Arm	None	None	
All three doses will be evaluated independently. Secondary analyses will compare doses; indication of a dose response will provide evidence of efficacy.

The remainder of this protocol amendment applies only to Stage 2. Please refer to [APPENDIX K](#) for more information on Stage 1 and [APPENDIX L](#) for Stage 1 Open Label Extension.

In the stage 2 study, all subjects completing 9 cycles of the originally assigned treatment may switch to an open label extension and receive PRM-151 10 mg/kg every 4 weeks. The first cycle of the open label phase contains a loading dose of 10 mg/kg on days 1, 3 and 5. This will allow for subjects from all three dosing cohorts to receive a loading dose of 10 mg/kg while maintaining the blind. Additionally, subjects who have entered the open label extension study prior to the approval of this amendment may receive a loading dose (10 mg/kg on days 1, 3, and 5), to be administered on their next scheduled cycle after approval of this protocol amendment. This will allow for these subjects to receive any potential pharmacologic benefit of the loading dose. As of 14-Nov 16, we have blinded safety data, although limited, on 21 patients receiving a similar 10 mg/kg loading dose in the open label of the PRM-151-202 IPF study after 24 weeks of exposure to PRM-151 or placebo in 2:1 ratio. No incremental risk has been reported in these subjects.

## 2. STAGE 2 STUDY OBJECTIVES

### 2.1 Primary Objective

The primary objective of this study is:

- To determine the effect size of three different doses of PRM-151 on reduction in bone marrow fibrosis by  $\geq 1$  grade in intermediate-1, intermediate-2, and high risk subjects with PMF, post-PV MF, or post ET-MF who are anemic or thrombocytopenic and who are ineligible for, intolerant of, or have had an inadequate response to ruxolitinib.

## **2.2 Secondary Objectives**

The secondary objectives of this study are:

- To determine if there is a difference in efficacy between the three doses of PRM-151 used in the study
- To evaluate the safety and tolerability of three different doses of PRM-151
- To assess the duration of effect of three doses of PRM-151 on reduction in bone marrow fibrosis
- To assess the effect and duration of effect of three doses of PRM-151 on disease related anemia, thrombocytopenia, and constitutional symptoms
- To assess IWG-MRT response (Complete Response, Partial Response, Clinical Improvement), stable and progressive disease in subjects treated with three doses of PRM-151

## **2.3 Exploratory Objectives**

The exploratory objectives of this study are:

- To measure changes in bone marrow fibrosis by quantitative image analysis and evaluate changes in bone marrow morphology in subjects receiving PRM-151
- To assess the effect of PRM-151 on other disease related parameters, including hematologic abnormalities and spleen size
- To assess the effect of PRM-151 on prognostic factors associated with increased mortality as measured by the DIPSS (Dynamic International Prognostic Scoring System)
- To evaluate the interaction between selected genetic mutations and cytogenetic abnormalities and response to PRM-151
- To explore potential biomarkers of PRM-151 activity in bone marrow samples
- To assess the effect of PRM-151 on bone marrow metabolism by PET imaging (at selected institutions)
- To evaluate the correlation of baseline PTX-2 levels with outcomes
- To evaluate the relationship between bone marrow fibrosis reduction and hematologic improvements in subjects treated with PRM-151
- To measure progression-free and overall survival in subjects receiving PRM-151

### 3. STAGE 2 STUDY ENDPOINTS

#### 3.1 Primary Endpoint

The Primary endpoint for the study is:

- Bone marrow response rate, defined as the percent of subjects with a reduction in bone marrow fibrosis score by at least one grade according to WHO criteria ([APPENDIX D](#)) at any time during the study as determined by a central adjudication panel of expert hematopathologists, blinded to subject, treatment, and time of biopsy

#### 3.2. Secondary Endpoints

The secondary endpoints for the study are:

- Comparison of primary and secondary efficacy parameters between doses
- Incidence of adverse events (AEs), serious adverse events (SAEs), and changes in laboratory test results
- Bone marrow improvement:
  - Bone marrow response rate at weeks 12, 24, and 36
  - Duration of bone marrow response
- Hemoglobin improvement

Baseline Status	Categories of Hemoglobin Improvement
Subjects who are transfusion dependent ( $\geq 2$ units PRBC every 4 weeks for 12 weeks prior to or after C1D1), regardless of baseline hemoglobin level	Percent of subjects with Red cell transfusion independence (no transfusions for $\geq 12$ consecutive weeks)  OR  50% reduction in RBC transfusions for $\geq 12$ consecutive weeks
Subjects with baseline hemoglobin $< 100$ g/L AND Not transfusion dependent	Percent of subjects with $\geq 10$ g/L and $\geq 20$ g/L increase in hemoglobin for $\geq 12$ consecutive weeks without transfusions

- Platelet improvement

Baseline Status	Categories of Platelet Improvement
Subjects who are transfusion dependent ( $\geq 2$ platelet transfusions in any 12 weeks prior to or after C1D1), regardless of baseline platelet level	Percent of subjects with: Platelet transfusion independence (no transfusions for $\geq 12$ consecutive weeks)  OR

Platelet transfusion = either 1 unit apheresed (single donor) platelets or 4-8 units pooled random donor platelets	50% reduction in platelets transfusions for $\geq$ 12 consecutive weeks
Subjects with $25 < \text{baseline platelets} < 50 \times 10^9/\text{L}$  AND Not platelet transfusion dependent	Percent of subjects with: Doubling of baseline platelet count for $\geq$ 12 consecutive weeks without platelet transfusions  OR  Platelet count $> 50 \times 10^9/\text{L}$ for $\geq$ 12 consecutive weeks without platelet transfusions,
Subjects with baseline platelet count $< 25 \times 10^9/\text{L}$  AND Not platelet transfusion dependent	Percent of subjects with: Doubling of baseline platelet count for $\geq$ 12 consecutive weeks without platelet transfusions  OR  Platelet count $> 25 \times 10^9/\text{L}$ for $\geq$ 12 consecutive weeks without platelet transfusions

- Hematologic improvement

Baseline Status	Categories of Hematologic Improvement
Subjects with both Hemoglobin $< 100 \text{ g/L}$ and Platelets $< 50 \times 10^9/\text{L}$	Percent of subjects who have EITHER Hemoglobin improvement OR Platelet improvement as described above and no worsening of hemoglobin or platelets from baseline
Subjects with only Hemoglobin $< 100 \text{ g/L}$	Percent of subjects who have Hemoglobin improvement as described above  AND Did not develop platelets $< 50 \times 10^9/\text{L}$
Subjects with only Platelets $< 50 \times 10^9/\text{L}$	Percent of subjects who have Platelet improvement as described above  AND Did not develop Hemoglobin $< 100 \text{ g/L}$ or new transfusion dependence

- Symptom improvement:

- Percent of subjects with 25% and 50% reduction in MPN-SAF Total Symptom Score from baseline at Week 36
- Mean change from baseline in EORTC QLQ-C30 at 36 weeks
- Duration of all improvement parameters listed above
- Percent of subjects with complete response, partial response, clinical improvement, stable disease, and progressive disease according to IWG-MRT criteria (Tefferi 2013, APPENDIX B)

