2.2.2 Secondary Efficacy Endpoints

The secondary efficacy endpoints are as follows for:

Stage 1:

- Bone Marrow MF grade shifts relative to baseline over time
- Modified Myeloproliferative Neoplasm-Symptom Assessment Form Total Symptom Score (MPN-SAF TSS) changes from baseline over time

Stage 2:

- Bone Marrow improvement:
 - Bone marrow (BM) response rate (MF Grade) at each visit (reduction of 1 grade versus baseline)
 - Duration of BM response defined for responding subjects as time from first decrease from baseline of one grade to time of return to baseline levels. If no return to baseline levels or worse than baseline then duration will be censored at the last BM assessment.
- Hemoglobin improvement (number and percentage of subjects):
 - For red blood cell transfusion dependent subjects at baseline (at least 2 units every 4 weeks for 12 weeks prior to Cycle [C]1Day [D]1), improvement is defined as either:
 - 1) absence of any packed red blood cells (PRBC) transfusion during any consecutive 12 weeks interval with hemoglobin level of ≥80g/L

OR

- 2) at least a 50% reduction in PRBC transfusions for 12 consecutive weeks with hemoglobin level of ≥80g/L
- For red blood cell transfusion independent subjects improvement is defined as:
 - ≥10 g/L increase in hemoglobin level for 12 consecutive weeks without transfusions
- Platelet improvement (number and percentage of subjects)

- For transfusion dependent subjects at baseline, improvement is defined as either:
- 1) becoming transfusion independent for 12 consecutive weeks

OR

- 2) reduction in transfusions need ≥50% from baseline for 12 consecutive weeks
- For transfusion independent subjects with baseline platelet count below 100^9/L, improvement is defined as:
 - ≥50% increase in the number of platelet for 12 consecutive weeks or normalization of platelet count (above lower limit normal)
- Symptom improvement:

Percent of subjects with 50% reduction in MPN-SAF TSS from baseline over time(Tefferi 2013)

• Percent of subjects with complete response, partial response, clinical improvement, stable disease and progressive disease according to IWG-MRT criteria.

2.2.3 Exploratory Efficacy Endpoints

The exploratory efficacy endpoints are as follows for:

Stage 1:

- Bone marrow biopsy results for:
 - Myeloblasts (%), at each time point and change from baseline
 - Cellularity (%), at each time point and change from baseline
 - Collagen and reticulin grade shifts relative to baseline over time

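### Near two platelet transfusions per 12 weeks, a 50% reduction scored on any 12-week stretch would count about 90% of unchanged subjects as improved

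*Protocol*

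**What the plan says.** Protocol 3.2 (Secondary Endpoints) treats a subject as platelet-transfusion dependent at two or more "platelet transfusions in any 12 weeks prior to or after C1D1". Improvement is either no transfusions, or a "50% reduction in platelets transfusions for" at least 12 consecutive weeks. The RBC rule has the same shape: dependence at two or more "units PRBC every 4 weeks for 12 weeks prior to or after C1D1", and improvement by independence or a "50% reduction in RBC transfusions for" at least 12 consecutive weeks. No calendar window is named for any of these. Elsewhere in the same list the protocol does fix a time: the symptom and QLQ-C30 endpoints are set at Week 36.

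SAP 2.2.2 keeps both limbs. For platelets it asks for a "reduction in transfusions need ≥50% from baseline for 12 consecutive weeks" and gives no number that defines dependence. For RBC it sets dependence before C1D1 and asks for "at least a 50% reduction in PRBC transfusions for 12 consecutive weeks", followed by a hemoglobin condition of at least 80 g/L. For RBC independence it states the floating window outright: no PRBC "transfusion during any consecutive 12 weeks interval with hemoglobin level of ≥80g/L". SAP 4.4.2 measures duration of improvement from the first 12-week improvement period, which also implies a floating window.

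There is no untreated arm: the table in Protocol 1.5 says the doses are evaluated independently. Protocol 10.6.1.3.2 reports per-arm rates with 95% confidence intervals. Protocol 10.6.1.3.4 tests doses pairwise at an unadjusted two-sided 0.05.

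**The concern.** One baseline count is compared with the lowest count found in any 12-week stretch on treatment. The baseline count has itself been selected for reaching the dependence threshold. At a baseline of 2, halving means at most one transfusion in the quietest stretch, and ordinary variation often supplies that. If most unchanged subjects score as improved, a high percentage in one dose arm says little about the drug. An inactive dose then sits close to the ceiling, so an active dose has little room to look better.

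**Working it through.** Neither document gives an expected or no-change rate for this endpoint, so there is no figure to reproduce. The only power figure, in Protocol 10.1, concerns bone marrow response.

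**Inputs from the documents.** Platelet dependence is at least 2 transfusions in 12 weeks. The improvement limbs are as quoted above. Treatment lasts 9 × 28 = 252 days. A 12-week window is 84 days, so the number of windows with different start days is 252 − 84 + 1 = 169.

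**Assumptions.** The true transfusion rate is constant, follow-up is complete, and gaps between transfusions are gamma-distributed with a coefficient of variation (CV) between 0.25 and 1.0, where 1.0 is Poisson.

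**Scoring.** A subject improves if count ≤ 0.5 × baseline count. A window with no transfusions always meets this, so for platelets the 50% limb contains the independence limb when both use the same window.

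**Hand check (Poisson, baseline equal to the true rate).** For one pre-set window, p = P(X ≤ rate/2). For three non-overlapping windows, the chance that at least one qualifies is 1 − (1 − p)³.
- Rate 2: p = e⁻²(1 + 2) = 0.406; three windows give 1 − 0.594³ = 0.79.
- Rate 4: p = e⁻⁴(1 + 4 + 8) = 0.238; three windows give 1 − 0.762³ = 0.56.
- Rate 12: p = P(X ≤ 6) = 0.046; three windows give 0.13.

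Allowing all 169 rolling windows raises these to 93%, 81% and 34%.

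**Simulation with a random baseline of at least 2: unchanged subjects scored improved (%).**

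| True rate per 12 weeks | Window | CV 1.0 | CV 0.7 | CV 0.5 | CV 0.3 |
|---|---|---|---|---|---|
| 2 | any | 94 | 93 | 91 | 89 |
| 2 | Weeks 25–36 | 46 | 37 | 29 | 17 |
| 4 | any | 73 | 58 | 40 | 16 |
| 4 | Weeks 25–36 | 24 | 14 | 7 | 1 |
| 6 | any | 59 | 39 | 21 | 2 |
| 6 | Weeks 25–36 | 16 | 8 | 2 | <1 |
| 12 | any | 34 | 13 | 2 | 0 |
| 12 | Weeks 25–36 | 6 | 1 | <1 | 0 |

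At CV 0.25 the any-window rate is 88–89% at 2 per 12 weeks and 7–8% at 4. Clustering works the other way. When the rate varies between 4-week blocks, the any-window figures are 79–86% at 4 per 12 weeks and 53–66% at 12.

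**RBC.** With 2-unit episodes, at least one in each 4-week block at baseline and no hemoglobin condition, the any-window rate is 32–93% at 6 units per 12 weeks, 2–68% at 12 units and 0–35% at 24 units (CV 0.3 to 1.0). The SAP's 80 g/L condition can only lower these, so they are upper bounds.

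**Discrimination at 2 platelet transfusions per 12 weeks, if the drug truly halves them.**
- Any window: 99.8% against 94% with no effect (CV 1.0), and 99.7% against 91% (CV 0.5). The gaps are about 6 and 9 points.
- Weeks 25–36: 78% against 46%, and 75% against 29%. The gaps are 32 and 46 points.

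**The case against.** **Most subjects.** A reader might infer that most unchanged subjects in the trial would count as improved. The documents do not support that. They give neither the distribution of baseline transfusion rates nor their regularity. At 4 or more per 12 weeks, whether the chance rate is a majority depends on the assumed variation. Early withdrawal would lower every figure.

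**RBC.** Nor can the platelet result be carried over to RBC. Dependence there needs about 6 units in 12 weeks (2 units in each of three 4-week periods), and the SAP adds the hemoglobin condition.

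**False dose differences.** A reader might also infer that the rule creates spurious differences between doses. It does not: the chance rate is the same in each randomised arm. Protocol 10.6.1.3.4 also warns that the unadjusted secondary tests need cautious reading.

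**Existing safeguards.** Transfusions in the 12 weeks before Week 36 are already summarised for dependent subjects (SAP 2.2.3). The protocol's composite hematologic endpoint adds no-worsening conditions. The IWG-MRT anemia response in Appendix B uses a rolling window but requires complete absence of PRBC after at least 6 units, closing with hemoglobin of at least 85 g/L. These help, but the first is exploratory, the composite is not listed in SAP 2.2.2, and Appendix B has no 50% limb and no platelet transfusion rule. None of them calibrates the stand-alone platelet rate.

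**Replacing the rule.** The any-window rule is not always worse. At 6 per 12 weeks and CV 0.5 it separates a halving drug from no effect by 97% against 20%, compared with 58% against 2% for Weeks 25–36. That argues for reporting both. Anchoring only the 50% limb would not be enough. With independence still scored on any window, 73–75% (CV 1.0) or 37–39% (CV 0.5) of unchanged subjects at 2 per 12 weeks would still count as improved.

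**Timing.** SAP section 1 says that an earlier Stage 2 SAP was signed before the Stage 2 primary database lock. That SAP is not available here and may have defined windows.

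**Conclusion.** The point holds near the platelet threshold. At a true rate of 2 per 12 weeks about 90% of unchanged subjects would score as improved under every regularity assumption tried. The chance rate is about 8–73% at 4 per 12 weeks. At 12 it is about one third or less for Poisson or more regular transfusion, and higher if transfusions cluster. RBC is less affected, by an amount the documents do not allow one to fix.

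The consequence is limited to two things: per-arm rates that cannot be read as drug effect without an untreated arm, and diluted dose differences near the threshold. All percentages rest on assumed rates and regularity, a constant true rate and full 36-week follow-up.

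**What to change.** In SAP 2.2.2 and 4.4.2, for transfusion-dependent subjects:
- Keep the any-window result, and report beside it an anchored version of the whole criterion. Score both independence and 50% reduction on Weeks 25–36 against the 12 weeks before C1D1, with subjects who leave early counted as not improved. This fits the non-responder rule in SAP 4.9.
- Restrict the anchored version to subjects whose dependence was established before C1D1, and state the platelet threshold, which SAP 2.2.2 omits. A subject who qualifies only after C1D1 may have a baseline of 0 or 1, for which halving would mean no transfusions at all.
- Compare doses on on-treatment transfusion counts with a negative-binomial model, using a log-exposure offset and baseline count and randomisation stratum as covariates.
- State that any-window per-arm rates near the threshold are not evidence of effect on their own.

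The cost is wording and programming, since the transfusion diaries are already collected (Protocol 7.11.2). The downside is that an early improvement lost by Week 25 does not count in the anchored version. Because earlier SAPs preceded the Stage 2 primary lock, label these analyses as added later.

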### 3.3 Exploratory Endpoints

The exploratory endpoints for the study include:

- Bone marrow:
  - Percent of subjects with Grade 0-1 bone marrow fibrosis grade at any time during the study and at weeks 12, 24, and 36
  - Duration of Grade 0-1 bone marrow fibrosis grade
  - Mean change from baseline to 12, 24, and 36 weeks in bone marrow fibrosis by quantitative image analysis
  - Changes from baseline to weeks 12, 24, and 36 in bone marrow metabolism by FDG or FLT PET scan (where feasible)
  - Assessment of changes in bone marrow morphology at 12, 24, and 36 weeks
- Hematologic and other disease related laboratory parameters:
  - Mean change from baseline to 36 weeks in: hemoglobin, # RBC units transfused in previous 12 weeks, platelet count, # platelet transfusions in previous 12 weeks, white blood cell count, absolute neutrophil count, reticulocyte count, peripheral blood blast count, and -lactic dehydrogenase (LDH)
  - Percent of subjects with increase in Hgb from  $< 100$  g/L to  $> 100$  g/L without transfusions, increase in platelets from  $< 50 \times 10^9$ /L to  $> 100 \times 10^9$ /L, decrease in WBC from  $> 25$  to  $< 25$ , increase in ANC from  $< 1500$  to  $\geq 1500$ , decrease in peripheral blood blasts from  $> 1\%$  to  $< 1\%$ , and disappearance of leukoerythroblastosis, at 36 weeks and for  $\geq 12$  weeks at any time during the study

- Duration of increase in Hgb from  $< 100\text{g/L}$  to  $> 100\text{g/L}$  without transfusions, increase in platelets from  $< 50 \times 10^9/\text{L}$  to  $> 100 \times 10^9/\text{L}$ , decrease in WBC from  $> 25$  to  $< 25$ , increase in ANC from  $< 1500$  to  $\geq 1500$ , decrease in peripheral blood blasts from  $> 1\%$  to  $< 1\%$ , and disappearance of leukoerythroblastosis
- Spleen improvement:
  - Percent of subjects with 10% and 35% reduction in spleen size from baseline by CT at 36 weeks
  - Duration of 10% and 35% reduction in spleen size from baseline
  - Mean change from baseline in spleen size by CT or MRI and palpation (in subjects with palpable spleen at baseline) at 36 weeks
  - Change in spleen and liver metabolism by FDG or FLT PET scan at 12, 24, and 36 weeks
- DIPSS:
  - Percent of subjects with a reduction in DIPSS score and category at week 36
  - Mean change in DIPSS score from baseline to Week 36
- Mutational Status and Cytogenetics:
  - Association of baseline mutational status of JAK2V617F, MPLW515, Calreticulin, ASXL1, EZH2, SRSF2, IDH1/2 with selected primary and secondary endpoints
  - Changes in allele burden of JAK2V617F at week 36. Changes in allele burden of MPLW515, Calreticulin, ASXL1, EZH2, SRSF2, IDH1/2 at week 36 will be measured as commercially available assays become available.
  - Association of baseline cytogenetic abnormalities and selected primary and secondary endpoints
- Association of baseline PTX-2 levels with selected primary and secondary endpoints
- Evaluation of potential biomarkers of PRM-151 activity in bone marrow biopsies taken at baseline, weeks 12, 24, and 36

- Measurement of progression-free and overall survival

